13.3 Monitoring

To minimize the risks of preoperative SBRT, safety will be monitored by A Bayesian stopping rule for the rate of acute toxicity grade ≥ 3 convincingly greater than 10%. Specifically, the Bayesian toxicity monitoring rule that suspends the accrual any time if the posterior probability of acute toxicity grade ≥ 3 risk being larger than 10% is 75% or higher. We assume a priori that this experimental regimen has an average risk around 5% and there is about 10% chance that the risk will be 10% or higher. This corresponds to a Beta (1,20) prior distribution. The following table gives the corresponding stopping rule for the 40 patients. For example, if 3 patients out of the first 5 treated patients experience acute toxicity grade ≥ 3 , we will suspend accrual temporarily and the principle investigators and study team will review the toxicity data and recommend either modification or termination of the trial.

# patients with toxicity	3	4	5	6	7
Out of total # patients treated	5	6-14	15-22	23-31	32-40

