2.2 SECONDARY OBJECTIVES

2.2.1 To determine the rate of severe acute toxicity, defined as any CTCAE v4 grade 3 or higher toxicity noted from RT delivery up to 90 days after completion of surgery.

2.2.2 To determine the rate of poor cosmetic outcomes from both provider and patient perspectives up to 3 years after pre-operative SBRT to intact breast tumors using the RTOG (Radiation therapy oncology group) cosmesis scale and digital images.

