6.5 SURGERY

Resection of the tumor will be completed 7-14 days after delivery of radiation. Surgery will include sentinel node assessment per our institutional standards, but omission of sentinel biopsy is permitted in patients age 70 and over with no clinical evidence of nodal involvement. Resection of the tumor must include a 2mm margin of normal tissue. A re-excision vs post-operative whole breast RT should be considered if the margin is less. Positive margins must be re-excised unless deemed technically not feasible by the surgeon (eg anterior margin dissected to skin).

6.6 PATHOLOGIC ASSESSMENT:

Standard pathologic assessment per our institutional guidelines will be followed and additionally will include RCB analysis and repeat evaluation of Ki67 and receptor status (ER, PR and HER2) if there is any residual invasive cancer.

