6.7.2 ADJUVANT SYSTEMIC THERAPY

Adjuvant systemic therapies including chemotherapy and endocrine therapy will be at the discretion of the medical oncologist. If Oncotype DX or other genetic scoring is desired for evaluation, this will be sent on the pre-treatment biopsy specimen obtained before enrollment on study and which was used for initial diagnosis. Medical oncology approval via case discussion or formal consultation is required prior to pre-operative SBRT to ensure the medical oncologist will be able to obtain all needed information to determine adjuvant systemic recommendations.

6.8 CRITERIA FOR DISCONTINUATION FROM PROTOCOL TREATMENT.

Because SBRT is delivered in one day, discontinuation is unlikely. However if at any time the constraints of this protocol are detrimental to the patient's health and/or the patient no longer wishes to continue on the study long-term, the patient shall be removed from the protocol follow-up. In this event the reason(s) for discontinuation of study participation will be noted by the PI in the Radiation Oncology record. Subjects who prematurely withdraw will not be replaced unless radiation has not been initiated. Reasons for PI-initiated withdrawal may include, but is not limited to the following:

- Adverse events
- Abnormal laboratory values
- Abnormal test procedure results
- Protocol deviation
- Administrative issues
- Disease progression

6.9 DURATION OF THERAPY:

The duration of protocol-specified therapy will be approximately 2 months. It is expected that treatment planning may take 2 weeks from simulation to treatment delivery, and that 4-6 weeks will elapse from treatment delivery to surgery.

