13.2 Analysis of secondary objectives

Acute toxicities (up to 90 days after completion of surgery) will be collected using CTCAE v4.0 and will be tabulated by body system, type and grade. The number and percentage of patients who experience at least one grade 3 or higher AE will also be reported. The presence or absence of all CTCAE toxicities included in Appendix 15.2 will be assessed in addition to those listed here: breast pain, dermatitis, atrophy, fatigue, fibrosis, lymphedema, pruritis, seroma, surgical wound dehiscence, fat necrosis, surgical site infection, hyperpigmentation, skin ulceration. We will use continuous toxicity monitoring throughout the trial as described below. Stopping rules are described below in 13.3.

Local recurrence rates will be calculated using cumulative incidence function, where death without local recurrence is considered as competing event. The associated 95% confidence intervals at landmark timepoints including 6 months, 1 year, 2 years and 3 years will also be provided.

Physician assessment of cosmesis (see Section 9.3) will occur at baseline, 4-6 weeks after surgery, 6 months, 1, 2 and 3 years. The secondary endpoint of poor cosmetic outcome is a physician-assessment of unacceptable (fair or poor) cosmesis at any time point through 3 years and/or occurrence of grade 3 or higher toxicity through 3 years. The number and percentage of patients, with 2-sided x% CIs, will be reported. The timepoint of unacceptable cosmesis assessment and of the grade 3 or higher AEs will be summarized descriptively. Additionally, when all enrolled subjects have had 1 year of follow-up, a working group of investigators will be assembled to evaluate cosmesis on all patients.

Patient-reported satisfaction with cosmetic outcome will be assessed at baseline, 6 months, 1, 2 and 3 years. Satisfaction over time will be summarized descriptively and graphically.

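### Section 13.3 does not say how patients still inside the acute-toxicity window count in the stopping table, and the table omits two early cells (3/3 and 3/4) that meet its own 75% criterion

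*Combined protocol and SAP*

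**What the plan says.** Section 13.3 sets a rule that "suspends the accrual any time if the posterior probability of acute toxicity grade" ≥3 risk exceeding 10% is at least 75%. On the prior it says: "This corresponds to a Beta (1,20) prior distribution". The boundary is printed as 3 toxicities at 5 patients, 4 at 6-14, 5 at 15-22, 6 at 23-31 and 7 at 32-40, and the denominator row is headed "Out of total # patients treated". The worked example suspends accrual if "3 patients out of the first 5 treated patients experience acute toxicity grade" ≥3. Crossing leads to a temporary suspension and a review by the study team.

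The monitored event is defined in 2.2.1 as "any CTCAE v4 grade 3 or higher toxicity noted from RT delivery up to 90 days after completion of surgery". Section 13.2 adds: "We will use continuous toxicity monitoring throughout the trial as described below". No section states how a treated patient who has not yet completed the window enters the count, and none sets a minimum number of patients before the rule applies.

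**The concern.** A grade ≥3 event counts on the day it occurs. A non-event is established only when the window closes. With continuous monitoring, the number treated therefore includes patients whose outcome is unknown, and a table indexed by number treated gives each of them full credit as a non-event. That pulls the posterior down and can postpone suspension when the true risk is well above 10%. This is the trial's only numerical safety rule, and the treatment is a single fraction that cannot be withdrawn, so the cost of a delay is patients treated before a review takes place.

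A second, smaller gap is that the text applies the 75% criterion from the start while the table begins at 5 patients.

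**Working it through.** **1. Reproducing the printed table.** The inputs, all from 13.3, are the Beta(1,20) prior, the 10% risk limit, the 75% threshold and a maximum of 40 patients. With x toxicities in n patients, the posterior is Beta(1+x, 20+n−x), and the boundary is the smallest x with P(risk > 0.10) ≥ 0.75. Checks at the column ends:

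| Column | Last n in column | Next n |
|---|---|---|
| 3 events | 3/5: 0.764 | 3/6: 0.741 |
| 4 events | 4/14: 0.7504 | 4/15: 0.731 |
| 5 events | 5/22: 0.760 | 5/23: 0.743 |
| 6 events | 6/31: 0.755 | 6/32: 0.739 |
| 7 events | 7/40: 0.752 | – |

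Every printed cell from n = 5 to n = 40 is reproduced.

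**2. Missing cells.** 3/3 gives Beta(4,20), posterior 0.807. 3/4 gives Beta(4,21), posterior 0.786. Both meet the criterion. The chance of at least 3 events in the first 4 patients is 4p³(1−p) + p⁴, which is 0.4% at p = 0.10 and 2.7% at p = 0.20. Three events by patient 3 or 4 are still three events at patient 5, so with immediate outcomes the suspension probability does not change (14.5% at 10% risk, 75.7% at 20%, both exact). Mean patients treated at 20% risk is 24.93 with the two cells and 24.97 without.

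**3. Pending patients: an example.** Suppose 10 patients are treated and 3 toxicities have occurred, all among the first 5. Indexed by all treated, this is 3/10: Beta(4,27), posterior 0.647, four events needed, accrual continues. Indexed by the first 5 treated, it is 3/5: Beta(4,22), posterior 0.764, accrual is suspended.

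**4. Size of the delay.** The window is 90 days plus the interval from SBRT to surgery. With the 7-14 days of 6.5 that is 97 to 104 days, taken here as 100. Accrual and onset are assumptions: 0.5 to 3 patients per month with exponential gaps, and onset uniform over 100 days. The simulation used 40,000 trials per scenario and checked the rule at each event. The same patients were used under both conventions, and 3/3 and 3/4 were included in both, so only the denominator differs. Treatment order means that accrual is suspended if, for any n, the events known so far among the first n treated reach the boundary for n. At 20% true risk:

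| Patients/month | Patients inside the window | Mean treated, all-treated | Mean treated, treatment order | Extra treated | Suspended before patient 40, all-treated vs treatment order | Ever crossing, all-treated |
|---|---|---|---|---|---|---|
| 0.5 | 1.6 | 26.05 | 25.55 | 0.5 | 71.9% vs 72.8% | 75.3% |
| 1 | 3.3 | 27.15 | 26.18 | 1.0 | 69.4% vs 71.4% | 74.6% |
| 2 | 6.6 | 29.18 | 27.47 | 1.7 | 64.1% vs 68.8% | 73.7% |
| 3 | 9.9 | 31.05 | 28.78 | 2.3 | 58.5% vs 66.1% | 73.1% |

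Ever crossing under treatment order is 75.9% in the simulation (75.7% exact), so the all-treated count loses at most 2.8 points. If onset is confined to the first 45 days, the extra patients treated are 0.2/0.5/0.9/1.3 at 0.5/1/2/3 per month.

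**The case against.** A reader might infer that the row heading and the worked example prescribe two contradictory denominators. The text does not support that. The example is offered as an illustration directly after the table and restates its first cell; when exactly 5 patients have been treated, the two wordings give the same number. What the documents show is an unstated convention for pending patients. The example's wording is compatible with treatment order but does not mandate it.

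It is also fair to say that neither convention is the 75% criterion itself, because the protocol never says what a pending patient contributes to the posterior. Calling the literal count late presumes that a pending patient should not get full credit as a non-event. That presumption follows from the 90-day definition in 2.2.1, but the plan does not state it.

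The operative sentence has no minimum n, so a team working from the text would already suspend at 3/3 or 3/4. That stands, and it makes the missing cells a matter of tidying the table.

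The size rests wholly on assumed accrual and onset. The study calendar places toxicity assessments within a week before surgery and 4-6 weeks after it. With the interval in 6.5, the later one falls about 35 (7 + 28) to 56 (14 + 42) days after SBRT, and the next is at month 6. Events can be recorded between visits (10.1), but this schedule makes the 45-day scenario, with its smaller delays, at least as relevant as the 100-day one.

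Finally, crossing leads only to a temporary suspension and review, and Sections 10.6 and 11 provide IRB and Safety Monitoring Committee oversight. This limits the consequence. Those sections give no numerical toxicity criterion, so they do not settle the denominator.

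**Conclusion.** The point holds as a minor clarification. The boundary arithmetic is right; the handling of patients still in the window is undefined, and two cells that meet the stated criterion are missing. Read literally, the table makes suspension slightly late, at 20% true risk by roughly 0.2 to 1 extra patients at 0.5 to 1 per month and about 1 to 2 at 2 to 3 per month, for 45- to 100-day onset. The effect is mainly later suspension rather than missed suspension.

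Two stronger conclusions might be drawn and are not supported. One is that the safety rule is miscalculated or ineffective: it reproduces exactly, and even at 3 per month with 100-day onset it is eventually crossed in 73.1% of trials at 20% risk. The other is that the conflict over the timing of surgery is part of this defect. Section 6.5 says "Resection of the tumor will be completed 7-14 days after delivery of radiation", whereas 6.9 expects that "4-6 weeks will elapse from treatment delivery to surgery". These passages must be reconciled, but that is a separate inconsistency. It bears on this point only through the window length: uniform onset over 125 days gives 0.6/1.2/2.0/2.6 extra patients at 0.5/1/2/3 per month.

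**What to change.** (1) In the 13.3 table, change the first column from 5 to 3-5.

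(2) Add one sentence so that pending patients are not counted as completed non-events. For example: *At each new grade ≥3 event the table is applied in treatment order; accrual is suspended if, for any n, the events known so far among the first n treated patients reach the boundary for n, whether or not later patients have been treated.*

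The prior, the threshold and all other cells stay as they are. Under treatment order, eventual crossing depends only on the sequence of outcomes by order of treatment, so the exact values of 14.5% at 10% risk and 75.7% at 20% hold for any accrual rate or onset pattern.

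The cost is slightly more temporary suspensions at 10% true risk. Before patient 40, at 0.5/1/2/3 per month, they rise to 13.5/13.0/12.4/11.7% from 12.6/11.3/9.3/7.4% with 100-day onset, and to 13.7/13.5/13.1/12.8% from 13.3/12.7/11.6/10.5% with 45-day onset. Some of these occur when event-free follow-up in later patients, credited by the fraction of the window completed, would put the posterior below 75%: about 5/10/15/20% of suspensions at 10% risk with 100-day onset, and about 1% with 45-day onset.

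Treatment order is one defensible convention, and the team may prefer another. The alternatives have costs too. Counting only patients with an event or a completed window raises eventual crossing at 10% risk to 17.6/19.8/24.5% at 1/2/4 per month, against 15.9% for treatment order in the same 3,000-trial simulation with a 104-day window. Weighting patients by completed follow-up reached 16.7% at 10% risk with 3 per month and 45-day onset. What matters is that 13.3 names one convention.

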Appendix 15.1 BCTOS

	Difference between treated and untreated breast and area			
	None	Slight	Moderate	Large
1. Breast size.....	1	2	3	4
2. Breast texture (hardening)	1	2	3	4
3. Arm heaviness.....	1	2	3	4
4. Nipple appearance.....	1	2	3	4
5. Shoulder movement	1	2	3	4
6. Arm movement	1	2	3	4
7. Breast pain.....	1	2	3	4
8. Ability to lift objects.....	1	2	3	4
9. Fit of shirt sleeve.....	1	2	3	4
10. Breast tenderness.....	1	2	3	4
11. Shoulder stiffness.....	1	2	3	4
12. Breast shape.....	1	2	3	4
13. Breast elevation (how high the breast is).....	1	2	3	4
14. Scar tissue.....	1	2	3	4
15. Shoulder pain.....	1	2	3	4
16. Arm pain.....	1	2	3	4
17. Arm swelling.....	1	2	3	4
18. Breast swelling.....	1	2	3	4
19. Arm stiffness.....	1	2	3	4
20. Fit of bra.....	1	2	3	4
21. Breast sensitivity.....	1	2	3	4
22. Fit of clothing.....	1	2	3	4

Appendix 15.2 CTCAE v. 4

https://evs.nci.nih.gov/ftp1/CTCAE/CTCAE_4.03_2010-06-14_QuickReference_5x7.pdf

Skin and subcutaneous tissue disorders					
Adverse Event	Grade				
	1	2	3	4	5
Rash maculo-papular	Macules/papules covering <10% BSA with or without symptoms (e.g., pruritus, burning, tightness)	Macules/papules covering 10 - 30% BSA with or without symptoms (e.g., pruritus, burning, tightness); limiting instrumental ADL	Macules/papules covering >30% BSA with or without associated symptoms; limiting self care ADL	-	-
Definition: A disorder characterized by the presence of macules (flat) and papules (elevated). Also known as morbilliform rash, it is one of the most common cutaneous adverse events, frequently affecting the upper trunk, spreading centripetally and associated with pruritus.					
Scalp pain	Mild pain	Moderate pain; limiting instrumental ADL	Severe pain; limiting self care ADL	-	-
Definition: A disorder characterized by marked discomfort sensation in the skin covering the top and the back of the head.					
Skin atrophy	Covering <10% BSA; associated with telangiectasias or changes in skin color	Covering 10 - 30% BSA; associated with striae or adnexal structure loss	Covering >30% BSA; associated with ulceration	-	-
Definition: A disorder characterized by the degeneration and thinning of the epidermis and dermis.					
Skin hyperpigmentation	Hyperpigmentation covering <10% BSA; no psychosocial impact	Hyperpigmentation covering >10% BSA; associated psychosocial impact	-	-	-
Definition: A disorder characterized by darkening of the skin due to excessive melanin deposition.					
Skin hypopigmentation	Hypopigmentation or depigmentation covering <10% BSA; no psychosocial impact	Hypopigmentation or depigmentation covering >10% BSA; associated psychosocial impact	-	-	-

Skin and subcutaneous tissue disorders					
Adverse Event	Grade				
	1	2	3	4	5
Definition: A disorder characterized by loss of skin pigment.					
Skin induration	Mild induration, able to move skin parallel to plane (sliding) and perpendicular to skin (pinching up)	Moderate induration, able to slide skin, unable to pinch skin; limiting instrumental ADL	Severe induration, unable to slide or pinch skin; limiting joint movement or orifice (e.g., mouth, anus); limiting self care ADL	Generalized; associated with signs or symptoms of impaired breathing or feeding	Death
Definition: A disorder characterized by an area of hardness in the skin.					
Skin ulceration	Combined area of ulcers <1 cm; nonblanchable erythema of intact skin with associated warmth or edema	Combined area of ulcers 1 - 2 cm; partial thickness skin loss involving skin or subcutaneous fat	Combined area of ulcers >2 cm; full-thickness skin loss involving damage to or necrosis of subcutaneous tissue that may extend down to fascia	Any size ulcer with extensive destruction, tissue necrosis, or damage to muscle, bone, or supporting structures with or without full thickness skin loss	Death
Definition: A disorder characterized by circumscribed, inflammatory and necrotic erosive lesion on the skin.					
Stevens-Johnson syndrome	-	-	Skin sloughing covering <10% BSA with associated signs (e.g., erythema, purpura, epidermal detachment and mucous membrane detachment)	Skin sloughing covering 10 - 30% BSA with associated signs (e.g., erythema, purpura, epidermal detachment and mucous membrane detachment)	Death
Definition: A disorder characterized by less than 10% total body skin area separation of dermis. The syndrome is thought to be a hypersensitivity complex affecting the skin and the mucous membranes.					

Appendix 15.3.1 RTOG cosmesis scale- PHYSICIAN FORM

1	EXCELLENT: when compared to the untreated breast or the original appearance of the breast, there is minimal or no difference in the size or shape of the treated breast. The way the breast feels (its texture) is the same or slightly different. There may be thickening, scar tissue or fluid accumulation within the breast, but not enough to change the appearance.
2	GOOD: there is a slight difference in the size or shape of the treated breast as compared to the opposite breast or the original appearance of the treated breast. There may be some mild reddening or darkening of the breast. The thickening or scar tissue within the breast causes only a mild change in the shape or size.
3	FAIR: obvious differences in the size and shape of the treated breast. This change involves a quarter or less of the breast. There can be moderate thickening or scar tissue of the skin and the breast, and there may be obvious color changes.
4	POOR: marked change in the appearance of the treated breast involving more than a quarter of the breast tissue. The skin changes may be obvious and detract from the appearance of the breast. Severe scarring and thickening of the breast, which clearly alters the appearance of the breast, may be found.

(Circle the number next to the word that best describes the cosmetic results.)

	None	Yes, present but does not affect cosmesis	Yes, present and affects cosmesis
Skin telangiectasia	0	1	2
Skin atrophy	0	1	2
Pigment change	0	1	2
Erythema	0	1	2
Fat necrosis	0	1	2
Fibrosis	0	1	2
Retraction or contour defect	0	1	2
Breast shrinkage	0	1	2
Other significant tx effects Specify: _____	0	1	2

October 10, 2023

Principal Investigator: [name]

IRB IRB00128074

Appendix 15.3.2 RTOG cosmesis scale- PATIENT FORM

1. How satisfied with your treatment are you?

Extremely satisfied Very satisfied Satisfied Unsatisfied

2. Would you choose this treatment again?

Yes No

3. Please circle the number that correlates with your assessment of the cosmetic result of your treatment:

1	EXCELLENT: when compared to the untreated breast or the original appearance of the breast, there is minimal or no difference in the size or shape of the treated breast. The way the breast feels (its texture) is the same or slightly different. There may be thickening, scar tissue or fluid accumulation within the breast, but not enough to change the appearance.
2	GOOD: there is a slight difference in the size or shape of the treated breast as compared to the opposite breast or the original appearance of the treated breast. There may be some mild reddening or darkening of the breast. The thickening or scar tissue within the breast causes only a mild change in the shape or size.
3	FAIR: obvious differences in the size and shape of the treated breast. This change involves a quarter or less of the breast. There can be moderate thickening or scar tissue of the skin and the breast, and there may be obvious color changes.
4	POOR: marked change in the appearance of the treated breast involving more than a quarter of the breast tissue. The skin changes may be obvious and detract from the appearance of the breast. Severe scarring and thickening of the breast, which clearly alters the appearance of the breast, may be found.
